The concept of offering greater removal of protein-bound uremic toxins and medium molecular weight molecules makes HD based on this type of medium cut-off membranes, generically called expanded hemodialysis (MCO), increase (expand) the clearance capacities of the membrane, constituting an important therapeutic step with which positive results have been obtained in some efficacy studies, aimed at evaluating inflammation, and the clearance of medium molecules (8).

Although current renal replacement therapy systems have reduced patient morbidity and mortality and significantly improved their quality of life, they have not achieved an efficiency equivalent to that of the kidney. New membranes for dialysis systems have recently been developed (medium cut -off membranes (COMs) that allow the filtration of medium molecular weight molecules and that, in some studies, have shown promising results. However, for this new technology, there is still little information from longitudinal studies with sufficient follow-up time on clinical outcomes of importance for the patient and health systems, such as survival, frequency of cardiovascular events or hospitalization.

This study aims to establish the role of serum albumin levels, as well as that of markers of inflammation and malnutrition on outcomes such as mortality, non-fatal cardiovascular

events, hospitalization and hospital days in patients on hemodialysis, treated with medium cut-off (MCO) or high flux (HD AF) membranes.

2. Objectives and outcomes

2.1. General objective

To establish the effect of serum albumin levels, as well as inflammation and malnutrition markers on outcomes such as mortality/survival, non-fatal cardiovascular events, hospitalization and hospital days in hemodialysis patients treated with medium cut-off (MCO) or high flux (HF) membranes.

2.2. Specific objectives

- 1. To describe the demographic and clinical characteristics of both cohorts (MCO and HD AF).
- 2. To estimate and compare the days of hospital stay and the incidence of mortality and hospitalization in the studied cohorts.
- 3. To compare the cumulative hospitalization time during participation in the study, between patients receiving MCO and those receiving HD AF.
- 4. To compare the time to death event between patients receiving MCO and those receiving HD AF.
- 5. To compare the frequency of non-fatal cardiovascular events in both cohorts.
- 6. To estimate the association between serum albumin levels and the outcomes mortality, non-fatal cardiovascular events, hospitalization events and days of hospital stay, controlling for the effect of third variables such as PEW, MIS, hs CRP, type of dialyzer.

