2.4. Primary Outcomes

Incidence of hospitalization events (per patient-year)

- Length of hospitalization (hospital days per patient-year)
- Mortality
- 4-year survival

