2.5. Secondary Outcomes

• Major non-fatal cardiovascular events

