⁵Austin PC, Stuart EA. (2017) The Performance of Inverse Probability of Treatment Weighting and Full Matching on the Propensity Score in the Presence of Model Misspecification When Estimating the Effect of Treatment on Survival Outcomes. Stat Methods Med Res, 26(4), 1654-1670

- 4. Evaluation of the balance of covariates: It will be carried out with graphical methods (QQ plots for continuous variables and bar graphs for nominal variables), and with descriptive numerical methods (standardized mean differences and variance ratios) and inferential methods (t tests and rank sum tests) ⁶.
- 5. Estimation of treatment effect: Treatment effects, according to the type of outcome, will be estimated using generalized linear models with weighting of the observations in the sample ⁷.
- 6. Sensitivity analysis: This analysis will be performed to determine the magnitude of the bias that may be produced by the omission of covariates. For this analysis, the methodology proposed by Carnegie, Harada, Dorie and Hill will be used ⁸.

In accordance with the specific objectives set out in the protocol, the following types of analysis are proposed:

- 1. For the objectives related to the comparison of time to hospitalization and time to death event between both cohorts, the respective incidence rates for each group and the survival functions will be calculated using Kaplan-Meier estimators.
 Comparisons between the survival functions of each of the two groups will be made with log- rank, Tarone-Ware or Peto-Peto Prentice tests, depending on the censoring pattern. Additionally, Cox models will be used to estimate the strength of association between type of treatment and time to event using the HRs metric.
 In these models, weighted samples will be used with the IPTW method and a group of time-dependent covariates will be incorporated (serum albumin, PEW, MIS, hs CRP, type of dialyzer).
- 2. To meet the objectives related to counting variables (days of hospitalization and non-fatal cardiovascular events), Poisson regression models or negative binomial

⁶Austin P.C. (2009) Balance diagnostics for comparing the distribution of baseline covariates between treatment groups in propensity-score matched samples. Stat Med 10;28(25):3083-107

⁷Austin P.C. (2016) Variance Estimation When Using Inverse Probability of Treatment Weighting (IPTW) With Survival Analysis. Stat Med. 35 (30), 5642-5655

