PEW	Mean (SD),	Mean (SD),	Mean (SD), Median
	Median (IQR)	Median (IQR)	(IQR)
PEW categorized			
0=No wear (0-2)	n(%)	n(%)	n(%)
1=With wear (>=3)	n(%)	n(%)	n(%)
Malnutrition-			
Inflammation Scale			
Hydration status			
0= No signs and	n/ 9/)	n/ 9/)	n/ 0/)
symptoms	n(%)	n(%)	n(%)
1=Edema below the	n/ 9/)	n/ 9/)	n/ 0/)
knees	n(%)	n(%)	n(%)
2=Edema above knees	n(%)	n(%)	n(%)

Karnofsky	Mean (SD),	Mean (SD),	Mean (SD), Median
	Median (IQR)	Median (IQR)	(IQR)
Nutritional assessment			
1	n(%)	n(%)	n(%)
2	n(%)	n(%)	n(%)
3	n(%)	n(%)	n(%)

^{*}Variables measured every 6 months

Table 7Hospitalization variables

Variable	HDx	HF-HD	HF-HD
Hospitalization yes	n(%)	n(%)	n(%)
or no	11(70)	11(70)	11(70)
Diagnosis in			
hospitalization			
1=Cat 1	n(%)	n(%)	n(%)
2=Cat2	n(%)	n(%)	n(%)
3=Cat3	n(%)	n(%)	n(%)
Major			
cardiovascular	n(%)	n(%)	n(%)
event yes or no			
Fatal cardiovascular	n(%)	n/ 0/)	n(%)
event yes or no	11(70)	n(%)	11(70)
COVID in	n(%)	n(%)	n(%)
hospitalization	11(70)	11(/0)	11(70)
Days of hospital	Mean (SD), Median	Mean (SD), Median	Mean (SD), Median
stay	(IQR)	(IQR)	(IQR)

Table 8Mortality variables*

	HDx	HF-HD	Total
Death yes or no	n(%)	n(%)	n(%)
Cause of death			
1=Cancer	n(%)	n(%)	n(%)
2= Cardiovascular	n(%)	n(%)	n(%)
3=Infectious	n(%)	n(%)	n(%)
4=Metabolic	n(%)	n(%)	n(%)
5=Respiratory	n(%)	n(%)	n(%)
6 = COVID	n(%)	n(%)	n(%)

7=Other	n(%)	n(%)	n(%)
8= Unknown	n(%)	n(%)	n(%)
Dialysis-related death yes or no	n(%)	n(%)	n(%)

^{*}Variables measured every 6 months

Table 9End-of-follow-up variables*

	HDx	HF-HD	Total
Reason for			
termination of			
follow-up			
1= Death	n(%)	n(%)	n(%)
2= Loss of tracking	n(%)	n(%)	n(%)
3= Change of			
health	n(%)	n(%)	n(%)
provider/insurer			
4= Recover kidney	n(%)	n(%)	n(%)
function	11(70)		
5= Suspension of	n(%)	n(%)	n(%)
treatment			
6= Transplant	n(%)	n(%)	n(%)
7= Dialyzer change	n(%)	n(%)	n(%)
8= Changed to DP	n(%)	n(%)	n(%)
9= End of study	n(%)	n(%)	n(%)

^{*}Variables measured every 6 months

4. Data extraction and preparation

After the measurement of variables and the collection of data are completed, the sponsor of the study must provide the analysis group with a file containing the results of the measurements of the variables considered in the project. It is recommended that this file be in a plain text format, preferably as comma-separated text (*. csv) or tab-separated text (*. txt). Additionally, the sponsor is required to provide a file with the variable dictionary that must contain the following information:

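### Objective 3 contradicts the per-patient-year primary outcome, cardiovascular events have no time base, and the count models for both outcomes state no person-time offset

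*SAP*

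**What the plan says.** **Hospital days.** SAP section 2.4 lists as a primary outcome "Length of hospitalization (hospital days per patient-year"), next to "Incidence of hospitalization events (per patient-year"). Both are rates. In section 2.2, however, objective 3 is "To compare the cumulative hospitalization time during participation in the study, between patients receiving MCO and those receiving HD AF", which is a total over whatever time each patient contributes.

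**Cardiovascular events.** Objective 5 is "To compare the frequency of non-fatal cardiovascular events in both cohorts", and section 2.5 gives only "Major non-fatal cardiovascular events". Neither has a time base. Section 3.1.1 speaks of the presence of such events, and Table 7 reports cardiovascular events as yes or no with n(%).

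**Model.** Section 3.1.2.2, second item of the analysis list, reads: "To meet the objectives related to counting variables (days of hospitalization and non-fatal cardiovascular events), Poisson regression models or negative binomial" regression if there is overdispersion. The candidate covariates for each outcome are serum albumin, PEW, MIS, hs CRP and dialyzer type. No offset or exposure term is mentioned. The first item of the same list does name incidence rates, for hospitalization and death.

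**Follow-up.** Table 9 has nine codes for the end of follow-up. The ninth is end of study. The other eight are early exits: death, loss, change of provider or insurer, renal recovery, suspension of treatment, transplant, "7= Dialyzer change", and change to peritoneal dialysis.

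**The concern.** A total during participation and a rate per patient-year are the same comparison only if the cohorts have the same mean follow-up. For hospital days the SAP states both and does not say which one the model estimates. For cardiovascular events it states neither, so the model as written is a regression on a bare count.

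In a bare count, a patient who dies at month 3 without an admission is a zero, exactly like a patient followed for 4 years without one. The error runs in an awkward direction: the cohort losing patients earlier has less time to accumulate days and events, and so could look better. Conversely, a cohort that survives longer could be penalised for it. A primary outcome and the only secondary outcome are involved.

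The propensity weighting does not settle this. It is meant to balance baseline covariates, whereas time on study is determined after cohort entry.

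**Working it through.** **1. The plan's own figure.** Section 3.1.5 (sample size) gives 90% power for an IRR of 0.82 in all-cause hospitalization, with 564 and 534 patients and a significance level of 0.05 (taken as two-sided). Baseline rate, follow-up and dispersion are not stated, so it can only be solved backwards.

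- Required variance of log IRR: (ln 0.82 / (1.960 + 1.282))² = 0.00375.
- Under Poisson, variance = 1/(564 × μ × 0.82) + 1/(534 × μ), where μ is expected control events per patient. This gives μ ≈ 1.08, or about 0.27 per patient-year over 4 years.

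That rate is attainable under Poisson, but the 90% can be neither confirmed nor refuted. The present point does not depend on it. The 0.82 serves below only as a yardstick, since it refers to hospitalizations and not to the two outcomes at issue.

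**2. What a count model without an offset estimates.** Let λ be the event (or day) rate and T the mean follow-up in a cohort. If rates are constant over time and the same in patients who leave and patients who stay, the mean count is λT. Hence

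count ratio = (λ₁/λ₀) × (T₁/T₀).

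With log follow-up as an offset, the model estimates λ₁/λ₀ alone.

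**3. Assumed mean follow-up, no true difference (λ₁/λ₀ = 1).** The SAP gives no follow-up by cohort, so these values are illustrative.

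| T₁ versus T₀ (years) | Count ratio |
|---|---|
| 2.6 vs 2.8 | 2.6/2.8 = 0.93 |
| 2.4 vs 2.8 | 2.4/2.8 = 0.86 |
| 2.2 vs 2.8 | 2.2/2.8 = 0.79 |

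**4. Assumed exit hazards.** With a constant exit hazard h and a 4-year cut-off (the horizon implied by the 4-year survival outcome), mean follow-up is (1 − e^(−4h))/h: 3.01 years at h = 0.15, 2.75 at 0.20, 2.53 at 0.25 and 2.33 at 0.30.

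| Exit hazards per year | Count ratio at true ratio 1 |
|---|---|
| 0.20 vs 0.15 | 0.915 |
| 0.25 vs 0.15 | 0.841 |
| 0.30 vs 0.15 | 0.774 |

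At equal hazards the ratio is 1.00: variation between patients alone does not bias it.

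**5. Yardstick.** Mean follow-up 18% shorter in one cohort gives a count ratio of 0.82 with no true effect. In the other direction, a true ratio of 0.82 in a cohort followed for 2.8 rather than 2.4 years would appear as 0.82 × 2.8/2.4 = 0.96.

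**The case against.** The strongest reply is that hospital days already have a person-time base in section 2.4, and that the outcome definition normally governs the analysis. That stands as far as it goes. A reader might infer that the SAP has settled on comparing raw totals for this primary outcome; it has not. The defect there is an unresolved contradiction with objective 3, plus an offset left unstated.

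Second, an offset is not a candidate covariate, so its absence from the covariate list proves little, and elsewhere the SAP works with incidence rates and an IRR. This is fair, and the accurate statement is that the offset is not stated. But an offset has to be specified. With one objective worded as a total, two analysts could fit different models and both claim to follow the plan. For cardiovascular events no per-patient-year definition exists from which an offset could be inferred.

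Third, a reader might take Table 9 as showing unequal follow-up between the cohorts, or count nine exit reasons. Eight codes are early exits and one is completion. The table shows that follow-up can vary between patients; it says nothing on whether it differs between cohorts.

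Fourth, Table 7 belongs to the descriptive component. Its per-patient means, medians and n(%) are ordinary summaries and not errors.

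Finally, the protocol, which is not at hand, may define a time base for cardiovascular events. That would not remove the contradiction within the SAP or the missing model specification.

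**Conclusion.** The point holds as a contradiction and an incomplete model specification that should be corrected before analysis. Objective 3 and section 2.4 describe different quantities for hospital days. Non-fatal cardiovascular events have no time base, and their count model, followed as written, mixes event rate with time on study.

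The bias is conditional on two things: no offset is fitted, and mean follow-up differs between cohorts. Under the assumed values above, the spurious ratio runs from 0.77 to 0.93, with 0.86 for 2.4 versus 2.8 years. These figures rest on constant rates, on equal rates in leavers and stayers, and on follow-up or exit hazards that the SAP does not give. They show what could happen. They do not support the inference that the primary result is biased.

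**What to change.** - **Section 2.2, objective 3:** reword to hospital days per patient-year, to match section 2.4.
- **Section 2.2, objective 5, and section 2.5:** define the outcome as non-fatal cardiovascular events per patient-year.
- **Section 3.1.2.2, count models:** state that both the hospital-days and the cardiovascular-event models include log(time from cohort entry to end of follow-up) as an offset, with coefficient fixed at 1.
- **Table 7:** add person-time, hospital days per patient-year and cardiovascular events per patient-year by cohort, alongside the existing summaries.
- **Limitation to record:** the offset corrects for unequal time at risk. It does not by itself address informative exit, in particular through death or dialyzer change; the SAP should say so and state how this will be examined.

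The cost is a few lines of SAP text and one model term. Entry and exit times are already needed for the survival analyses, so no new data are required.

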2.3. Exploratory objective

1. Describe the use and type of nutritional supplements in the evaluated cohorts.

2.4. Primary Outcomes

Incidence of hospitalization events (per patient-year)

- Length of hospitalization (hospital days per patient-year)
- Mortality
- 4-year survival

2.5. Secondary Outcomes

• Major non-fatal cardiovascular events

2.6. Exploratory Outcomes

• Use and type of oral nutritional supplements .

3. Statistical analysis:

3.1. General information

3.1.1. Descriptive component:

This study includes demographic variables, medical history, hemodialysis treatment, laboratory parameters, medication, nutritional variables, variables related to hospitalization, variables related to mortality, and end-of-follow-up variables. The descriptive component will be carried out taking into account the continuous, ordinal, or nominal nature of the above variables, taking into account the following procedures:

 Continuous variables: Means or medians will be used as numerical methods to describe variables, along with their corresponding dispersion measures: standard deviation (SD) or interquartile range (IQR). Box plots will be used as graphical methods to evaluate the shape of the distribution, as well as to assess the

- presence of symmetry and extreme values. Normal quantile graphs will be used as a tool to assess the normality of the variables.
- Ordinal variables: Medians (IQR) or absolute and relative frequency measures will be used as summary measures in the case of variables with six or fewer modalities.
 Bar graphs will be used as summary graphic methods.
- 3. Nominal and count variables: Absolute frequencies and percentages will be used for their description using numerical methods. The summary graphic component will be carried out using bar graphs.

For the outcome variables (time between cohort entry and death, time between cohort entry and hospitalization, presence of non-fatal cardiovascular events, and days of hospitalization) their estimators will be calculated together with their 95% confidence intervals.

Each of these analyses will be performed for the entire sample, as well as for each of the exposure groups (MCO and HD AF).

3.1.2. Analytical component:

3.1.2.1. Bivariate analysis

1. Since there is no random assignment to treatments, these analyses will be performed to compare baseline characteristics between the two groups and to assess differences between variables with repeated measures, over time. The variables that will be incorporated into these analyses will be: Analysis are Albumin, PEW, MIS, hs CRP, dialyzer type. Longitudinal analysis of covariance will be used considering that in this approach the outcome variable, which is measured during different time periods, is adjusted by the baseline value.

3.1.2.2. Multivariate analysis

Considering that the results of analyses that include effect measures may be compromised by potential confounding bias given the non-experimental design of the study, it has been

proposed that statistical models incorporate propensity score analyses using inverse probability of treatment weighting (IPTW) methods. These analyses will have the following steps:

These analyses will have the following steps 1:

- 1. Data preparation: This stage includes the selection of covariates, and the assessment of data balance and the pattern of missing data. Not only the variables that are associated with the type of dialysis and with each of the outcomes used in this research will be selected, but also those that are associated only with the outcome, since it has been reported that this decision can increase the power to evaluate the treatment effect ². In the event that the handling of missing data is required, multiple imputation methods with chained equations will be carried out, carrying out the imputation separately in each exposure group ³.
- 2. Propensity score (PS) estimation: Given the dichotomous nature of the exposure, these scores will be estimated using logistic regression methods ⁴.
- 3. Application of the PS method: As mentioned before, the IPTW method will be applied, considering that it has advantages such as sample size optimization (it does not eliminate observations that cannot be matched) and versatility for its use with different multivariate analysis methods ⁵.

¹Austin PC, Stuart EA. (2015) Moving towards best practice when using inverse probability of treatment weighting (IPTW) using the propensity score to estimate causal treatment effects in observational studies. Stat Med 10;34(28):3661-79.

²Cuong, N. V. (2013). Which covariates should be controlled in propensity score matching? Evidence from a simulation study. Statistica Neerlandica, 67(2), 169–180.

³Puma, MJ, Olsen, R.B., Bell, S.H., & Price, C. (2009). What to do when data are missing in group randomized controlled trials. Washington, DC: National Center for Education Evaluation and Regional Assistance, Institute of Education Sciences, US Department of Education.

⁴Setoguchi, S., Schneeweiss, S., Brookhart, MA, Glynn, RJ, & Cook, E.F. (2008). Evaluating uses of data mining techniques in propensity score estimation: A simulation study. Pharmacoepidemiology and Drug Safety, 17(6), 546–555.

⁵Austin PC, Stuart EA. (2017) The Performance of Inverse Probability of Treatment Weighting and Full Matching on the Propensity Score in the Presence of Model Misspecification When Estimating the Effect of Treatment on Survival Outcomes. Stat Methods Med Res, 26(4), 1654-1670

- 4. Evaluation of the balance of covariates: It will be carried out with graphical methods (QQ plots for continuous variables and bar graphs for nominal variables), and with descriptive numerical methods (standardized mean differences and variance ratios) and inferential methods (t tests and rank sum tests) ⁶.
- 5. Estimation of treatment effect: Treatment effects, according to the type of outcome, will be estimated using generalized linear models with weighting of the observations in the sample ⁷.
- 6. Sensitivity analysis: This analysis will be performed to determine the magnitude of the bias that may be produced by the omission of covariates. For this analysis, the methodology proposed by Carnegie, Harada, Dorie and Hill will be used ⁸.

In accordance with the specific objectives set out in the protocol, the following types of analysis are proposed:

- 1. For the objectives related to the comparison of time to hospitalization and time to death event between both cohorts, the respective incidence rates for each group and the survival functions will be calculated using Kaplan-Meier estimators.
 Comparisons between the survival functions of each of the two groups will be made with log- rank, Tarone-Ware or Peto-Peto Prentice tests, depending on the censoring pattern. Additionally, Cox models will be used to estimate the strength of association between type of treatment and time to event using the HRs metric.
 In these models, weighted samples will be used with the IPTW method and a group of time-dependent covariates will be incorporated (serum albumin, PEW, MIS, hs CRP, type of dialyzer).
- 2. To meet the objectives related to counting variables (days of hospitalization and non-fatal cardiovascular events), Poisson regression models or negative binomial

⁶Austin P.C. (2009) Balance diagnostics for comparing the distribution of baseline covariates between treatment groups in propensity-score matched samples. Stat Med 10;28(25):3083-107

⁷Austin P.C. (2016) Variance Estimation When Using Inverse Probability of Treatment Weighting (IPTW) With Survival Analysis. Stat Med. 35 (30), 5642-5655

⁸Carnegie, N.B., Harada, M., Dorie, V., & Hill, J. (2016). treatSens: Sensitivity analysis for causal inference. Retrieved from https://cran.r-project.org/web/packages/treatSens/index.html

regression models will be used in case of overdispersion in the outcome variable. Within these models, the covariates that will be candidates for inclusion in the models are:

- a. For the outcome days of hospitalization: Serum albumin, PEW, MIS, hs CRP, dialyzer type
- 3. For non-fatal cardiovascular events outcome: Serum albumin, PEW, MIS, hs CRP, dialyzer type
- 4. For the objective related to the estimation of the association between serum albumin levels and the outcomes of mortality, non-fatal cardiovascular events, hospitalization events and days of hospital stay, the use of linear mixed models for longitudinal data is proposed. This strategy allows modeling the association between repeated measurements of independent variables and the proposed outcomes, in the presence of other variables that also vary over time. These models involve the combination of fixed effects and random effects models, and allow the inclusion of variables that change over time. To identify potential confounding variables, a directed acyclic causal diagram (DAG) will be performed. Additionally, G methods will be used for longitudinal data, which allow estimating the causal effect of an exposure that varies over time (in this case albumin levels) in the presence of confounding variables that also vary over time (hs CRP, MIS, PEW, FRR, type of dialyzer) that are in turn affected by the exposure. These methods may be more robust than traditional regression-based methods. The parametric G- formula and the weighted inverse probability of treatment estimation with marginal structural models 9will be used 10.11

⁹James M. Robins, Sander Greenland, Fu-Chang Hu. Estimation of the Causal Effect of a Time-Varying Exposure on the Marginal Mean of a Repeated Binary Outcome, J Am Stat Assoc. 1999; 94:447, 687-700.

¹⁰Miguel A Hernán, Babette Brumback, James M Robins. Marginal Structural Models to Estimate the Joint Causal Effect of Nonrandomized Treatments. J Am Stat Assoc. 2001; 96:454, 440-448.

¹¹Sally Picciotto, Miguel A. Hernán, John H. Page, Jessica G. Young, James M. Robins. Structural Nested Cumulative Failure Time Models to Estimate the Effects of Interventions. J Am Stat Assoc. 2012;107:499, 886-900.

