3.1.5. Handling missing data

Considering that in the present study data from a standardized clinical registry of proven quality in previous research will be used, a low amount of missing data is expected in the study variables. However, it is noted that the amount or pattern of missing data may affect the quality of the statistical estimates. Missing data and the mechanism by which they occur will be evaluated: MCAR (Missing Data). completely at random), MAR (Missing at random) and MNAR (Missing not at random), according to this evaluation, the appropriate data imputation procedures will be defined for each case

3.1.5 . Sample size:

Based on the availability of the assembled cohorts of 1098 patients, 564 on MCO in the Theranova® dialyzer cohort and 534 on conventional HD in the AF dialyzer cohort. This provides 90% power considering an IRR 0.82 for all-cause hospitalization and a significance level of 0.05 (26).

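### Kaplan-Meier for time to hospitalization, with no competing-risk method, overstates the probability of admission because patients who die first can only be censored

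*SAP*

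**What the plan says.** Analysis item 1 of SAP section 3.1.2.2 opens with "For the objectives related to the comparison of time to hospitalization and time to death event between both cohorts" and gives both endpoints the same treatment: "the respective incidence rates for each group and the survival functions will be calculated using Kaplan-Meier estimators". The groups are to be compared with log-"rank, Tarone-Ware or Peto-Peto Prentice tests, depending on the censoring pattern". The regression step is that "Cox models will be used to estimate the strength of association between type of treatment and time to event using the HRs metric", fitted in the IPTW-weighted sample.

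Section 3.1.1 lists "time between cohort entry and hospitalization" among the outcome variables to be estimated with 95% confidence intervals. Section 2.4 includes mortality and "4-year survival" among the primary outcomes. Table 9 codes death as the first reason for the end of follow-up, in the same list as loss to follow-up, transplant, dialyzer change and end of study.

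The SAP mentions no cumulative incidence function, Gray test, subdistribution model, cause-specific interpretation or composite with death. It gives no rule for handling death in the hospitalization analysis.

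**The concern.** Kaplan-Meier assumes that a censored patient could still have the event later, at the same rate as those still under observation. For a patient lost to follow-up that may be tenable. For a patient who has died it is not, because death makes a first admission impossible. For time to death the estimator is appropriate. For time to hospitalization its complement estimates the risk in a hypothetical population in which nobody dies, and that exceeds the proportion who are actually admitted.

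Two things are at stake. The absolute risk read from each curve is too high, increasingly so towards 4 years. The gap between the cohorts in absolute risk can also be wrong, because the error depends on each cohort's mortality. Mortality is itself a primary outcome compared between the cohorts, so equal death hazards cannot be taken for granted.

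**Working it through.** The SAP gives no figure for hospitalization risk or mortality, so there is no plan figure on this point to reproduce. The hazards below are assumptions and are taken as constant over time.

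**Inputs**
- Horizon t = 4 years, from the survival outcome in section 2.4; t = 1 year for comparison.
- h, hazard of first hospitalization: 0.3, 0.5 and 0.8 per year (assumed).
- d, hazard of death before any hospitalization: 0.03 to 0.25 per year (assumed). This is not total mortality, and may be lower.

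**Formulas**
- What Kaplan-Meier targets when deaths are censored: 1-KM = 1 - exp(-h t).
- Actual probability of admission (cumulative incidence): CIF = h/(h+d) × [1 - exp(-(h+d) t)].

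**Worked case**, h = 0.5, d = 0.12, t = 4:
- 1-KM = 1 - exp(-2.0) = 86.5%.
- CIF = 0.5/0.62 × [1 - exp(-2.48)] = 0.8065 × 0.9163 = 73.9%.
- Excess = 12.6 points.

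**Range at 4 years**

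| h | 1-KM | CIF, d = 0.03 | CIF, d = 0.10 | CIF, d = 0.20 | CIF, d = 0.25 | Excess (points) |
|---|---|---|---|---|---|---|
| 0.3 | 69.9% | 66.6% | 59.9% | 51.9% | 48.5% | 3.3 to 21.4 |
| 0.5 | 86.5% | 83.0% | 75.8% | 67.1% | 63.3% | 3.5 to 23.1 |
| 0.8 | 95.9% | 92.9% | 86.5% | 78.5% | 75.1% | 3.0 to 20.9 |

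The excess is positive in every case. At 1 year it runs from 0.4 points (h = 0.3, d = 0.03) to 5.5 points (h = 0.8, d = 0.25), so the long horizon matters.

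**Comparison between cohorts at 4 years.** Take h = 0.50 in the high-flux cohort and 0.50 × 0.82 = 0.41 in the MCO cohort, borrowing the rate ratio of 0.82 from the sample-size section for illustration only. The 1-KM difference is 86.5% - 80.6% = 5.9 points, whatever the mortality.

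| d, high flux | CIF difference, equal d | CIF difference, d 20% lower on MCO |
|---|---|---|
| 0.05 | 5.9 points | 4.8 points |
| 0.10 | 5.8 points | 3.9 points |
| 0.15 | 5.8 points | 3.1 points |

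With equal mortality the difference is essentially preserved, although both levels are too high. With unequal mortality it is not.

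**Equal admission hazards, unequal mortality.** With h = 0.5 in both cohorts and d = 0.12 against 0.18, 1-KM is 86.5% in both, while the cumulative incidences are 73.9% and 68.7%. The cohort with the higher death hazard has the lower probability of admission, simply because more of its patients die first.

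**The case against.** Several objections carry weight.

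- **Reach.** The primary hospitalization outcomes in section 2.4 are events and days per patient-year, and the power statement rests on a rate ratio. This mechanism does not inflate them. Time to hospitalization is not a listed primary outcome or a named specific objective; it appears in section 3.1.1 and in analysis item 1. This stands and limits the importance of the point.
- **Tests and hazard ratios.** Log-rank-type tests and Cox models with death censored validly compare the cause-specific hazard of admission. In the last example above, equal Kaplan-Meier curves correctly reflect equal admission hazards. This stands: the fault lies in reading the curve as an absolute risk.
- **Cumulative incidence can also mislead.** The same example shows a higher death hazard making a cohort look better on hospitalization, and a Fine-Gray hazard ratio can move the same way. This stands. It is why the curves belong beside the mortality results and why a subdistribution model should be optional.
- **Inference about censoring.** The SAP does not state that deaths are censored, nor that 1-KM will be reported as a probability. True, but plain Kaplan-Meier with no other rule leaves no other way to enter a patient who dies before admission, and a survival function for hospitalization is naturally read as a risk.

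Two stronger readings are tempting, and the SAP supports neither. A reader might infer that the same bias affects "Major non-fatal cardiovascular events". Section 3.1.2.2 analyses these as counts with Poisson or negative binomial regression and plans no Kaplan-Meier curve for them. A reader might also call the bias large because mortality is high in this population. The SAP gives no mortality figure, and the hazard that matters is that of death before a first admission.

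**Conclusion.** The point holds for the Kaplan-Meier curves of time to hospitalization. Followed as written, the plan overstates the probability of hospitalization whenever any patient dies before a first admission. The excess is about 3 to 23 percentage points at 4 years under the assumed constant hazards (0.3 to 0.8 per year for first admission, 0.03 to 0.25 per year for death before admission); where this study falls in that range cannot be determined from the SAP. The difference in absolute risk between the cohorts is misstated if their mortality differs, and nearly unchanged if it does not. Kaplan-Meier for all-cause death is not in question. The change is worth making, because the SAP names an estimator that does not estimate the risk of admission and a better one is readily available.

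**What to change.** In analysis item 1 of section 3.1.2.2, separate the two endpoints.

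1. **Time to death:** keep Kaplan-Meier.
2. **Time to first hospitalization:** replace Kaplan-Meier with IPTW-weighted Aalen-Johansen cumulative incidence curves by cohort, with death before admission as the competing event, and state that rule explicitly.
3. **Cox model for hospitalization:** label the weighted hazard ratio as cause-specific.
4. **Reporting:** show the hospitalization curves and hazard ratio beside the mortality results, so that a lower cumulative incidence caused by more deaths is not taken for a benefit.
5. **Optional:** a Fine-Gray model as a supplement.

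The cost is a few sentences in the SAP and modest extra Stata code. No new data are needed, since the plan already covers time to hospitalization, time to death and the reason for the end of follow-up.
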